Appendix I Physician Interview Guide

Physician Semi-Structured Interview

To be administered right after verbal consent.

Thank you for agreeing to be a part of this study.

Our dietary intervention consists of giving bladder cancer patients 3 things: 1) educational materials by mail, 2) One 20 minute phone call with a trained staff member to go over the educational materials, and 3) 11 automated phone calls that ask patients to report the servings of vegetables they ate in the previous week, with automated feedback based on the number of servings reported.

If our study shows that this intervention significantly reduces bladder cancer recurrence in bladder cancer patients:

1. To what extent would you welcome such an intervention?
Probe: What would make you like this intervention more?
2. To what extent would you think the intervention would be a good match for your clinic?
Probe: What would make this intervention fit better within your clinic?
3. To what extent do you think the intervention would be doable in your clinic?
Probe: What would make this intervention easier for your clinic to use?

That concludes the interview. Thank you so much for your time.

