8. STUDY ENDPOINTS

Primary Endpoint(s)

- Urinary ITC levels will be measured using HPLC-based cyclocondensation assay^{14, 51}, which measures ITCs and metabolites as low as a few picomoles and has been routinely performed in [name] laboratory. The results will be adjusted by urinary creatinine level using creatinine assay kits (Caymen, Ann Arbor, MI). Cruciferae intake will be assessed using a questionnaire adapted from Thomson et al.⁵² to capture both intake and cooking styles.

Secondary Endpoint(s)

- Gene expression will be evaluated via RNA-seq as a surrogate for intermediate efficacy, conducted at Roswell Park's Genomics Shared Resource using NextSeq500 platform (Illumina Inc.). We have worked with the Genomics core to optimize the extraction of RNA samples from urine. With the addition of TRIzol™ right before the storage of the cell pellet samples, we were able to extract sufficient amounts of RNA and generate high quality RNA-seq data. Dietary intake will be evaluated by three non-consecutive 24-hour dietary recalls (two weekdays, one weekday) conducted by trained staff using the interview-administered Nutrition Data System for Research (NDSR)⁵³.
- Additional urinary metabolites and potential biomarkers will be explored using proteomic and/or metabolomic approaches.

Exploratory Endpoint(s)

- Our exploratory endpoint will be identification of barriers, facilitators, and other process-related measures relevant to informing the implementation of an evidence-based cruciferae intervention within clinical practice.

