
Control intervention. Participants in the control arm will receive mailed materials about general fruit and vegetable intake intervention based on published NCI guidelines. (<https://cancercontrol.cancer.gov/ocs/>). The control intervention will utilize the same delivery method (i.e. mailed educational materials, live phone call, IVR calls) and follow the same contact schedule as the treatment schedule (See Appendix P and Appendix Q). We intend to compare our tailored cruciferae program with general program on increase of fruit and vegetable intake. We anticipate minimal contamination between intervention and control because BCS will be recruited throughout our catchment area and our intervention will be delivered individually with each BCS.

Personnel Training. [name] will utilize her extensive experience in training others in the delivery of behavioral interventions to train project staff to implement the intervention. A training-of-trainers model that incorporates didactic education, trainee practice, and written and verbal feedback will be used. Training will build knowledge about behavior change promotion, with a specific emphasis on delivering the live phone call with fidelity, utilizing participant booklets to program the IVR messages, and communicating effectively with participants about health. The training will conclude with project staff demonstrating mastery of concepts through mock phone sessions and live phone calls, and accurate programming based on booklet data received. Project staff will be asked to complete a checklist of topics to monitor intervention fidelity.

Aim 2: Conduct a feasibility pilot of our evidence-based dietary behavioral intervention

Study Design. We will use a Hybrid I implementation randomized-controlled design to simultaneously gather outcomes regarding the intervention's feasibility and process data to facilitate wide-spread implementation and dissemination of the intervention into clinical practice if the intervention is effective. A total of 80 patients will be recruited on a rolling basis. Forty will be randomized to intervention and 40 to control.

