We will ask intervention participants to nominate physicians to participate in a short 15-minute semi-structured interview. Research staff will mail an invitation letter to nominated physicians that will include an information sheet (Appendix J), opt-in/opt-card card, and stamped reply envelope. Within 2-weeks, physicians who do not respond will be contacted by phone, fax, or email with no more than 5 attempts. Participating physicians will receive \$100. Physicians who verbally consent to participate will be asked to refer other physicians to the study. CAB members will also utilize their networks to nominate physicians for staff to contact.

We will conduct brief 15-minute semi-structured interviews using an interview guide. The guide will give physicians a brief overview of our cruciferae intervention. Research staff will then ask questions regarding facilitators and barriers of intervention adoption within clinical practice³⁷. Staff will ask physicians the needed implementation strategies to sustain the intervention post research funding, in addition to intervention modifications to maximize sustained clinic adoption³⁷.

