Appendix U. Invitation Letter for Physician Interview and Opt-In/Out Card

Date

Dear Dr. X,

Your patient or colleague recently participated in the POW-R Health research study, a National Cancer Institute (NCI)-funded study that is testing different dietary strategies to lower the risk of bladder cancer recurrence. We are excited about this study because it may produce a dietary intervention that helps reduce the risk of bladder cancer recurrence and improve bladder cancer survivorship. To be noted, the funded study is a behavior intervention program that has no relevance to clinical treatment regardless of whether clinical care is provided.

We are contacting you because either your patient or colleague nominated you to be a part of this study. To be part of the study, all we need is to conduct a 15-minute phone interview with you to gain a physician's insight on how our dietary intervention—if proven to be successful—could be incorporated into routine care. Physicians who participate will receive a \$100 gift card from a local store as a small token of our appreciation.

If you can participate in a 15-minute phone interview, please let us know by filling out the card included in this mailing. If you do not want to participate, please let us know on the card so we do not contact you in the future.

For more detailed information about the study, please review the included information sheet.

Thanks so much for our consideration. We hope to hear from you soon.

Sincerely,

[name]
Professor
Cancer Prevention and Control
Roswell Park Comprehensive Cancer Center

[name]
Associate Professor
Cancer Prevention and Control
Roswell Park Comprehensive Cancer Center

Yes, I'm interested in participating in the phone interview. Please call me at: _____ during the following days and times:

No, I'm not interested in participating. Please do not contact me again about this study.

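### The physician interview guide omits the cruciferae overview that Section 11 says it will give, so the script does not prompt content-specific barriers

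*Combined protocol and SAP*

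**What the plan says.** Section 11 (Exploratory Aim) sets out what the guide is for: "The guide will give physicians a brief overview of our cruciferae intervention". It continues: "Research staff will then ask questions regarding facilitators and barriers of intervention adoption within clinical practice". Physicians are also to be asked which modifications would help clinics adopt the intervention and keep using it. Section 8 defines the exploratory endpoint as "identification of barriers, facilitators, and other process-related measures relevant to informing the implementation of an evidence-based cruciferae intervention within clinical practice", and Section 1 says the feedback will be used to refine the intervention.

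The guide in Appendix I calls the programme a dietary intervention with three parts: materials sent by mail, one 20-minute call with staff, and "11 automated phone calls that ask patients to report the servings of vegetables they ate in the previous week", with feedback that depends on the answer. It then asks whether the physician would welcome such a programme, whether it matches the clinic, and whether it is doable there. Each question has one probe.

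For the comparator, Section 11 states: "The control intervention will utilize the same delivery method (i.e. mailed educational materials, live phone call, IVR calls"), on the same contact schedule. The invitation letter in Appendix U describes the study only as "testing different dietary strategies to lower the risk of bladder cancer recurrence" and refers the physician to an enclosed information sheet (Appendix J).

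**The concern.** What sets the tested programme apart from its comparator is content: a particular group of vegetables, a daily goal for that group, and advice on which to choose, how to prepare them and when to eat them. Delivery is deliberately the same in both arms. A physician who hears only about delivery and vegetables can judge whether a clinic could run a mail-and-telephone programme. That physician has not been given, by the script, anything on which to judge whether this dietary content raises problems or advantages in practice. The exploratory endpoint and the planned refinement are both about the cruciferae intervention, so part of what they need is left unprompted. Analysis cannot later recover answers to questions that physicians were not placed to consider.

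**Working it through.** There is no figure to reproduce; the check is a comparison of texts. The intervention and control columns come from Section 10 (Table 1), Section 11, and the materials and scripts in Appendices P and Q. The last column is the overview in Appendix I.

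| Feature | Intervention | Control | Told to physician in the guide |
|---|---|---|---|
| Delivery | Mail, one live call, 11 automated calls | Same | Yes |
| Food counted | Cruciferous vegetables | Fruit and vegetables | Vegetables, unspecified |
| Daily goal | One serving of cruciferae | Separate fruit and vegetable goals | No |
| Choice | Medium or high isothiocyanate yield | Variety | No |
| Preparation | Raw or lightly cooked | Many methods | No |
| Timing | Dinner or late evening | None given | No |
| Track book | 24 copies | 24 copies | No, but it does not separate the arms |

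1. **Section 11 against Appendix I.** Section 11 places the cruciferae overview in the guide. The guide contains none of the words cruciferous, cruciferae, power vegetables or isothiocyanate. The two contradict each other whatever other documents say.

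2. **What the guide conveys.** Of the five content features that separate the arms (food counted, goal, choice, preparation, timing), four are absent. The fifth is conveyed only in that fruit is not mentioned.

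3. **Whether the omission looks intended.** The Community Advisory Board guide (Appendix L, item 7) names cruciferous vegetables and gives examples. The documents give no reason, such as masking, to withhold this from physicians.

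4. **Reach.** One script serves every interview. Recruitment is capped at 20, and the plan's own inputs (Section 19) give (40 + 5 + 5) × 0.48 = 24 willing physicians, so the cap is the relevant number.

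5. **Length of the live call.** The guide says 20 minutes. Sections 10 and 11 say about 45 to 60, and the call scripts in Appendix Q about 60. The length told to physicians is therefore 20/60 = 33% to 20/45 = 44% of the length stated elsewhere. This bears directly on whether a clinic finds the programme doable.

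**The case against.** Four arguments can be made against the point.

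**Physicians may learn the content elsewhere.** They are mailed Appendix J before the interview, Section 30 says telephone follow-up may use a script that mirrors it, and the guide is administered right after verbal consent. The text of Appendix J was not available for this review. A reader might infer that physicians do not know the programme concerns cruciferous vegetables; the documents do not support that. What remains is that Section 11 assigns the overview to the guide, and no step checks that the mailed sheet was read.

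**The questions suit a clinic-level aim.** A reader might infer that the interviews cannot yield barriers and facilitators of the cruciferae intervention. That goes too far. Mail, a live call and automated calls are how that intervention is delivered; the three questions with their probes address acceptance, fit and feasibility of that package; and a semi-structured format lets a physician ask more. This objection stands for delivery. It does not cover content, although Section 11 also asks physicians for modifications to the intervention.

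**Choice, preparation and timing are matters for the patient.** Patients' views are collected in the follow-up questionnaire (Appendix G1) and the cruciferous-arm feedback (Appendix G2), and survivors on the advisory board are interviewed (Appendix L). This limits the loss. It does not replace the physician's view, which is the stated endpoint.

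**The guide does not describe the control programme.** A reader might infer that the overview fits both arms equally well. It does not: control calls count fruit as well as vegetables, and the guide mentions no fruit. The delivery format is shared; the content is only partly indistinguishable.

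**Conclusion.** The guide omits an overview that the protocol says it will contain, and the endpoint is specific to the programme left undescribed. The consequence is bounded. Clinic-level delivery barriers remain obtainable, subject to the unreconciled call length. Barriers and facilitators specific to the cruciferae content are not prompted by the script, and answers may partly reflect a generic vegetable programme. How far they do depends on Appendix J and on what physicians ask, neither of which can be judged from the available text.

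All interviews (up to 20) are affected. The aim is exploratory and qualitative; randomisation, the primary and secondary endpoints and their analyses are untouched. The change is worth making because it costs very little and brings the script into line with the sponsor's own stated purpose.

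**What to change.** In the overview in Appendix I:

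- Change *servings of vegetables* to *servings of cruciferous vegetables (for example broccoli, cabbage, arugula)*.
- Add one or two sentences summarising the programme's daily goal and its advice on choice, preparation and timing, as worded in the participant materials.
- Reconcile the stated length of the live call with Sections 10 and 11 and Appendix Q.
- Check that Appendix J agrees with the revised overview.

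If interviews have already been held with the present wording, report exactly what physicians were told, from the guide and Appendix J together, and limit the conclusions accordingly. Do not relabel those interviews outright as answers about a general vegetable programme, because Appendix J may have named cruciferae.

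The cost is a minor amendment and less than a minute of a 15-minute interview. Sample size and analysis do not change.

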- Engage the clinical care providers of patients enrolled in our intervention to ascertain the barriers and facilitators of intervention implementation within clinical practice through conducting 20 semi-structured interviews. The goal is to gain feedback and refine the intervention for “real-world” implementation.

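### The physician interview guide has no direct question on barriers and none on sustaining the program, and it puts every question under a recurrence result that the trial has no plan to test

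*Combined protocol and SAP*

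**What the plan says.** Section 1 sets the exploratory objective: to "ascertain the barriers and facilitators of intervention implementation within clinical practice through conducting 20 semi-structured interviews". Section 8 defines the matching endpoint as "identification of barriers, facilitators, and other process-related measures relevant to informing the implementation" of the program in practice.

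Section 11, under the Exploratory Aim, says how this will be done: "We will conduct brief 15-minute semi-structured interviews using an interview guide". It then lists the content. First, "Research staff will then ask questions regarding facilitators and barriers of intervention adoption within clinical practice". Next, "Staff will ask physicians the needed implementation strategies to sustain the intervention post research funding", together with changes to the program that would help clinics keep using it. Section 19 plans a content analysis of the transcripts for barriers and facilitators.

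Appendix I is the guide. It describes the program briefly and then states a condition: "If our study shows that this intervention significantly reduces bladder cancer recurrence in bladder cancer patients". Three numbered questions follow. They ask how far the physician would welcome the program, how well it would match the clinic, and, third, "To what extent do you think the intervention would be doable in your clinic". Each has one probe, asking what would make the program better liked, a better fit, or easier to use. The guide then closes the interview.

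**The concern.** The guide is the instrument for the exploratory endpoint, and it is narrower than the section that describes it. If staff follow it as written, one promised topic (sustaining the program) is never raised. Another (barriers) depends on what a physician happens to say when asked about fit and feasibility. Interviews would then differ in whether barriers came up at all, and silence on a barrier could not be told apart from its absence.

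The premise is a separate matter. Every answer is given on the assumption that this study has shown fewer recurrences. The trial's outcomes are cruciferous vegetable intake, urinary isothiocyanates (ITC) and gene expression. For a clinician, lack of evidence on recurrence is a plausible reason not to adopt a program, and the premise removes that reason before the first question. Process data for later implementation are a stated purpose of the Hybrid I design in Section 9, so this affects something the trial was set up to learn.

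**Working it through.** No arithmetic applies beyond counting. The check sets each topic promised in Section 11 beside the three questions and three probes of Appendix I.

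| Topic promised in Section 11 | Direct prompt among 3 questions | Direct prompt among 3 probes | Coverage |
|---|---|---|---|
| Facilitators of adoption | 0 | 3 | Covered by the probes |
| Barriers to adoption | 0 | 0 | Indirect only, through match, doability and their probes |
| Strategies to sustain the program after funding | 0 | 0 | None |
| Modifications for sustained clinic use | 0 | 3, in part | Partial: improvements are asked for, but not in terms of continued use |

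So one of the four topics is fully covered, one in part, one indirectly and one not at all.

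**Is the guide complete as published?** It has an introduction, numbered questions and a closing sentence. Pages removed elsewhere in the document do not explain the gap.

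**How far does the premise reach?** It stands once, above question 1, and governs all three questions (3 of 3). No question is asked without it.

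**Could the trial produce the result named in the premise?**
- Section 8 lists urinary ITC and cruciferous intake as primary endpoints. Gene expression, dietary recalls and further urinary markers are secondary, and the physician process measures are exploratory. Recurrence is not listed.
- Section 19 has no analysis of recurrence, and the sample size rests on ITC and intake.
- Appendix G1 asks participants at 6 months whether the cancer has come back and includes an item on progression. The information is therefore collected, by self-report, but no comparison of it is planned.

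The trial is thus neither designed nor planned to show a significant reduction in recurrence, although it does record some recurrence data.

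**The case against.** The case for the guide has four parts.

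*Barriers can still emerge.* The interviews are semi-structured, and Section 19 allows for findings that emerge in coding. A physician who says the program is not very doable, or who names what would make it easier, is describing an obstacle from its other side. This stands. A reader might infer that barriers will not be measured at all, or that the analysis can report only what was literally asked; the documents do not support either. What remains is that barriers have no direct prompt, although Section 11 says staff will ask about them.

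*The endpoint is wider than barriers and facilitators.* Section 8 also names other process-related measures. Welcome, good match and doable echo the acceptability, appropriateness and feasibility items put to participants in Appendix G1, which suggests a deliberate choice. This also stands: the three questions are useful and should stay. It does not supply the missing sustainment question.

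*Assuming benefit is legitimate.* Section 9 speaks of implementation if the program proves effective, and the invitation letter in Appendix U uses a similar condition. Holding benefit fixed separates clinic-level obstacles from doubts about efficacy. That is a fair reason to keep an effectiveness scenario. It does not justify attributing the recurrence result to this study, or making it the only scenario offered.

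*No bias has been shown.* Correct. A reader might infer that the premise demonstrably pushes physicians toward acceptance. That is plausible, but nothing in the documents establishes it. Nor is it right to say that the premise describes an impossible result, since recurrence is self-reported at 6 months.

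**Conclusion.** The point holds as a mismatch between the guide and the plan. Appendix I does not fully deliver the content in Section 11: sustainment is absent, barriers are reached only indirectly, modifications are partly covered and facilitators are covered. In addition, 3 of 3 questions depend on a recurrence result for which the trial has no endpoint and no planned analysis. Answers may therefore be more favorable than they would be for a program shown only to change diet and urinary ITC. The size of any such shift cannot be estimated from the documents.

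The mismatch applies to every interview run from this guide, up to 20. It does not touch the primary or secondary outcomes, and the aim is exploratory, so the consequence is limited to what the trial can say about implementation. Correction is still worthwhile because the missing topics are ones the protocol itself promises. The conclusion assumes that interviewers follow the guide as written. If they add questions of their own, coverage may be better, but it would vary between interviews.

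**What to change.** In Appendix I:

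1. Add one direct barrier question, for example: *What would get in the way of using this program in your clinic?*
2. Add one sustainment question, for example: *What would your clinic need to keep it running after research funding ends?*
3. Reword the premise so that it does not attribute a recurrence result to this study. One option is to ask the questions first on what the trial measures, namely cruciferous intake and urinary ITC. The other is to keep the recurrence scenario as an explicit hypothetical about future evidence.

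While the guide is open, its description of the live call also needs attention. Appendix I gives 20 minutes, Section 11 gives about 45 to 60, and the call scripts in Appendix Q give about 60. Physicians judging feasibility need one figure, so these passages must be reconciled.

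The cost is two more questions and one reworded sentence, with a minor amendment. The interview becomes slightly longer, which matters a little when it is advertised as 15 minutes. Any interviews already done used the existing guide, so the version used should be recorded for each physician and taken into account in the content analysis.
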